**4.6 Consent Procedures****A. Consent**▪ **Documenting Consent**

Please see Attachment 4.

▪ **Waiver of Documentation Of Consent**

N/A

▪ **Waiver or Alteration of Consent Process**

N/A

**B. Consent Process**▪ **Location of Consent Process**

The Consent Process will take place at the Cook-Douglass Student Health Center of the New Jersey Institute for Food, Nutrition & Health

▪ **Ongoing Consent**

N/A

▪ **Individual Roles for Researchers Involved in Consent**

Co-Investigators [name] and [name], or graduate student [name] (with supervision) will conduct the consent process to explain all aspects of the study and answer any questions the prospective participants may have. [name], [name] or [name] will sign the consent form.

**1. Consent Discussion Duration**

It is expected that the consent discussion will last approximately 30 min.

**2. Coercion or Undue Influence**

In order to minimize the possibility of coercion or undue influence, the consent process will not be conducted by research personnel who have any known relationship or conflict of interest with the prospective participants.

**3. Subject Understanding**

Throughout the consent process the prospective participants will be encouraged to ask any questions should they feel the need to do so. The consent process will be divided into a series of small sections. Members of the research team will summarize each section, use probe questions to check for sufficient understanding before proceeding to the next section.

**4.7 Special Consent/Populations**

N/A

**4.8 Economic Burden and/or Compensation for Subjects****A. Expenses**

The participants will likely incur expenses when they travel to our research facilities.

**B. Compensation/Incentives**

Participants will be paid up to \$60. The compensation is based on the amount of time that the participants is expected to spent in our research facilities and is calculated according to the minimum wage in New Jersey in 2017. They will have to successfully complete all food testing sessions to receive full compensation. The payment schedules are as follow:

- \$20 when they complete Week 2
- \$40 when they return the CGM sensor at the end of the study

Should participants choose to withdraw from the study, no pro-rata payment will be made other than the ones scheduled above.

The compensation will be paid in the form of gift cards.

#### **4.9 Risks to Subjects**

##### **A. Description of Subject Risk**

The finger prick test and the use of CGM sensor both involve piercing of the skin which may cause infection. However infection is rare.

Participants may experience gastrointestinal symptoms (e.g. bloating, flatulence, diarrhea, constipation or cramping) when they consume the fiber-supplemented test food. These discomforts are common, however, these discomforts are minor and they should not last longer than a few hours.

##### **B. Procedures for Risks to Embryo, Fetus, and/or Pregnant Subjects**

N/A

##### **C. Risks to Non-Subjects**

N/A

##### **D. Assessment of Social Behavior Considerations**

- Reasonably Foreseeable Risks

N/A

- Risk Of Imposing An Intervention On Subject With Existing Condition

N/A

- Other Foreseeable Risks

N/A

- Observation And Sensitive Information

N/A

##### **E. Minimizing Risks**

Participants will be advised to drink enough fluids throughout the food testing day (approximately eight 8-ounce glasses of fluid a day) to avoid constipation.

##### **F. Certificate of Confidentiality**

N/A

##### **G. Potential Benefits to Subjects**

Participants will receive reports of their daily fluctuations of blood glucose level throughout the study.

##### **H. Provisions to Protect the Privacy Interests of Subjects**

Should any participants desire not to interact with or provide personal information to specific members of the research team, they may report such a need to the Principal Investigator and the arrangement of the research personnel will be adjusted accordingly. Participants will not be required to provide a reason if they desire not to do so. Should changing of the research personnel is not possible, the Principal Investigator will discuss with the participants about alternative solutions.

In order to ensure the protection of personal health information of the participants, there will be no identifiable information on any of the data collection instruments. Each participant will be assigned a unique identification code. A master code identifier which links the identification code and personal information (name, date of birth and contact information) will be maintained separately from the study data. Only the Principal Investigator and approved research personnel who have a specific need for identifiable information will have access (e.g. Study Physician to communicate directly with participants and/or their primary physicians; research student/staff to schedule appointments). All data and materials collected during this study are for research purpose only, and the data will be kept in strict confidence. No information will be given to anyone without permission from the participants.

***I. Research Team Access To Subject Data***

A code will be assigned to every participant and the collected data will be recorded using the participant's unique code for identification purposes. Only the Principal Investigator, Study Physician and research staff/student who schedule appointments will have access to the master code identifier and be able to re-identify the participants if necessary. Each member of the research team will only be able to have access to the subsets of study data (in de-identified form) that are relevant to his/her scope of work.

**4.10 Secondary Data – Records/Chart Reviews/Databases/Tissue Banks/etc.**

N/A

**4.11 Chart/Record Review Selection**

N/A

**4.12 Secondary Specimen Collection**

N/A

**5.0 Special Considerations**

**5.1 Health Insurance Portability and Accountability Act (HIPAA)**

N/A

**5.2 Family Educational Rights and Privacy Act (FERPA)**

N/A

**5.3 NJ Access to Medical Research Act**

N/A

**5.4 Code of Federal Regulations Title 45 Part 46 (Vulnerable Populations)**

N/A

**6.0 Research Data Protection and Reporting**

**6.1 Data Management and Confidentiality**

**A. Data analysis plan:** Statistical analyses will be performed using the SPSS Statistics Software Package. Analysis of variance with Tukey's post-hoc test (two-tailed) will be used for intra-and inter-group comparisons of postprandial blood glucose concentration (area-under-curve). Independent-samples *t* test (two-tailed) will be used to analyze variations in other participant characteristics. Statistical significance will be accepted at *p* value < 0.05.

**B. Quality control:** All research personnel will complete CITI training and be knowledgeable about Good Clinical Practice (GCP), relevant regulations and policies. The Principal Investigator will ensure adherence to the study protocol, regulatory requirements, GCP standards at all times. Team meeting will be held on a regular basis to review adherence to study protocol, and to discuss any incidents of failures of protocol compliance, keeping adequate and accurate records, and reporting of adverse events.

**C. Data handling:** The study data will include two key components: 1) a master code identifier that contains the personal information of the participants and the participant code assigned to them; and 2) study data files that contain all the de-identified data generated in this trial. Participants' hard copy files will be kept in locked cabinets only accessible by authorized research personnel in a secured building. Electronic files will be password-protected and stored on the university's secure server and will only be accessible to authorized research personnel. The master code identifier and the data files will be kept in two separate locations. The master code identifier is only accessible to the Principal Investigator, Study Physician and research staff who schedule appointments and the study data files are accessible to authorized research personnel who work in relevant components of the trial. Data in hard copies and the master code identifier will be kept for 6 years after study completion, thereafter they will be shredded. As data will then exist in de-identified form, the electronic data files will be kept indefinitely. The Principal Investigator will be responsible should receipt and/or transmission of data is required. All data transported/shared will be de-identified.

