### 1.5 Sample Size Justification

No power calculation is performed for this pilot study. We aim to have 5 completers in the Non-Diabetes and 5 in the Prediabetes/Diabetes group, for each of the test panel (i.e. a total of 20 completers). This sample size is comparable to those used in published pilot studies on bran products. Steinert et al (7) used 10 participants (healthy, overweight and obese) to examine the effect of oat bran on glycemic response; Sheflin et al (8) used 7 participants (3 in control and 4 in experimental group) to examine the effect of heat-stabilized rice bran on gut microbiota and metabolites.

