**C. Require Number of Subjects to Complete Research**

20 (5 each in Panel A Non-Diabetes group and Prediabetes/Diabetes group, same two groups for Panel B)

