**D. Feasibility Of Recruiting**

We expect to recruit the majority of our participants from the New Brunswick campus of Rutgers University. With a relatively flexible study schedule and no particularly stringent eligibility criteria, we do not anticipate difficulties in engaging interest in the Rutgers community. We expect a recruitment rate of 4-6 participants per week over 4-6 weeks including an estimated attrition rate of 20%.

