**G. Tests for Safety Data**

Pearson Chi-square tests (two-tailed) will be used to compare the safety data (e.g. number of reported adverse events) after consuming the control food (white bread) and each of the test food to determine whether the dietary fiber supplementation is causing harm comparing to an everyday food item.

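### The AUC analysis has no participant effect and no rule for people who stop early, although 20% attrition is expected over 14 sessions on seven foods

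*Combined protocol and SAP*

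**What the plan says.** Section 1.3 gives each participant seven foods, white bread and six fiber-supplemented items. Each is tested on two consecutive days, which makes 14 sessions in four weeks. Section 4.5 A enrols 24 people. Section 4.5 C gives the number who must complete as "20 (5 each in Panel A Non-Diabetes group and Prediabetes/Diabetes group, same two groups for Panel B", which matches section 1.5: "We aim to have 5 completers in the Non-Diabetes and 5 in the Prediabetes/Diabetes group, for each of the test panel". Section 1.5 also says "No power calculation is performed for this pilot study". Losses are expected in section 4.5 D: "We expect a recruitment rate of 4-6 participants per week over 4-6 weeks including an estimated attrition rate of 20"%.

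The analysis of the glucose outcome is one sentence in section 6.1 A: "Analysis of variance with Tukey's post-hoc test (two-tailed) will be used for intra-and inter-group comparisons of postprandial blood glucose concentration (area-under-curve". It does not say whether the ANOVA is one-way or repeated-measures, does not name participant as a factor, defines no analysis set, and gives no rule for a person with AUCs for some foods only. The only readable text on withdrawal, in section 4.8 B, concerns payment.

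For safety, section 6.3 G plans chi-square tests "to compare the safety data (e.g. number of reported adverse events) after consuming the control food (white bread) and each of the test food".

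**The concern.** The comparison of foods is within person: the same people eat bread and the test foods. Someone who stops partway leaves AUCs for some foods and none for others. The sentence in section 6.1 A can be run in two ordinary ways, and each handles that person badly.

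- **Listwise repeated-measures ANOVA.** A person missing any food is removed, so all their completed tests are lost. The cells are meant to hold 5 people, and the result then describes only those who got through all 12 fiber servings (six foods, twice each).
- **Ordinary ANOVA on all AUCs.** The tests are kept, but between-person variation goes into the error term. Foods tested early are averaged over more people than foods tested late. If stoppers have different glucose levels and bread sits early or late, part of a food-versus-bread difference is a difference between people.

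With nothing specified, the choice would be made after the data are seen. Stopping could be related to the foods, because section 4.9 A describes gastrointestinal symptoms after the fiber foods as common. The pilot is meant to guide food development for a later study in type 2 diabetes (section 1.1 A), so the contrasts should be as clean as the design allows.

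**Working it through.** **1. The plan's own count.** Inputs: 20 completers (section 1.5: "i.e. a total of 20 completers") and 20% attrition (section 4.5 D).

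- 20 × (1 + 0.20) = 24, the stated enrolment.
- 20 / (1 − 0.20) = 25.
- 24 × 0.80 = 19.2 expected completers.

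So 24 is reproduced, and four or five people with incomplete data are what the plan expects.

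**2. Share of collected AUCs that come from stoppers.** Let d be attrition and f the average fraction of the 14 sessions done before stopping. Then share = d·f / ((1 − d) + d·f). The documents do not give f, so it is an assumption.

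| d | f (assumed) | Share of AUCs |
|---|---|---|
| 20% | 1/14 | 0.0143 / 0.8143 = 1.8% |
| 20% | 0.25 | 0.05 / 0.85 = 5.9% |
| 20% | 0.50 | 0.10 / 0.90 = 11.1% (1 in 9) |
| 20% | 0.75 | 0.15 / 0.95 = 15.8% |
| 20% | 13/14 | 0.1857 / 0.9857 = 18.8% |
| 4 of 24 (16.7%) | 0.50 | 28 / (280 + 28) = 9.1% (1 in 11) |

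The last row uses 20 × 14 = 280 AUCs from completers and 4 × 7 = 28 from stoppers.

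**3. Precision lost by analysing completers only.** Simulation of one cell of 6, with seven foods tested twice and 20% stopping after a session drawn uniformly from 1 to 13. Assumed, not from the documents: between-person SD 25, within-person SD 15 or 25, true fiber-minus-bread effect −20. The table gives the SE of the mean food-minus-bread contrast in two separate runs.

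| Order | Within-person SD | Completers only | Participant-effect model, all tests |
|---|---|---|---|
| Bread first | 15 | 5.45; 5.33 | 4.89; 4.88 |
| Bread first | 25 | 8.87; 8.90 | 8.05; 7.97 |
| Random | 15 | 5.43; 5.35 | 5.08; 5.04 |
| Random | 25 | 8.85; 8.93 | 8.39; 8.33 |

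The ratios run from 8.85 / 8.39 = 1.05 to 8.90 / 7.97 = 1.12, an SE about 5–12% larger.

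**4. Bias of an ordinary ANOVA on all AUCs.** Assume bread comes first and stoppers run one between-person SD (25) higher. A stopper is present at session k with probability (14 − k)/13.

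- Bread (sessions 1–2): (1 + 12/13)/2 = 0.962. Stoppers' share of the bread mean is 0.2 × 0.962 / (0.8 + 0.2 × 0.962) = 0.194, which raises it by 0.194 × 25 = 4.8.
- Other foods (sessions 3–14): (11 + 10 + … + 0)/(13 × 12) = 66/156 = 0.423. Stoppers' share is 0.2 × 0.423 / (0.8 + 0.2 × 0.423) = 0.096, which raises the mean by 2.4.
- Bias in food minus bread: 2.4 − 4.8 = −2.4, which is 2.4/20 = 12% of the assumed effect, in favour of fiber.

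The simulations agree: −2.4 to −2.6 for the ordinary ANOVA and about −0.2 to −0.6 for the participant-effect model. With food order random, the bias is about zero.

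**The case against.** The strongest reply is that the plan is silent rather than wrong. Section 6.1 A says only analysis of variance, and an ANOVA with participant as a factor would keep partial data and compare foods within person. That is true, but the plan does not name that analysis, and the two default readings both do worse.

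Several stronger readings are tempting, and the documents do not support them.

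- **That only completers will be analysed.** Sections 1.5 and 4.5 C set a recruitment target in completers; section 6.1 A does not restrict the analysis to them.
- **That one AUC in nine is affected.** That needs stoppers to finish half their sessions on average. Section 4.5 D gives the 20% as part of a recruitment forecast and does not say when people are lost. Someone lost before the first test leaves no AUC at all.
- **That the contrasts will be biased.** This needs stoppers who differ and an unbalanced order. Section 1.3 refers the schedule to Figure 1, which could not be read for this review. Even in the unfavourable case, the bias is less than half the SE of that estimator (about 6 to 9).
- **That adverse events of people who stop would be discarded.** The plan does not say so. Section 6.3 D collects safety data from the first food test onward and after each visit, section 6.3 B has the monitoring committee review retention and adverse events, and section 6.3 G compares events after each food, which naturally covers anyone who ate it.

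It is also fair that a 5–12% larger SE is modest in a pilot with no power calculation. That limits the weight of the point; it does not remove it, since the better analysis needs no extra data.

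A last objection concerns the remedy. A mixed model with participant as the only random effect treats the two tests of a food as independent. In a simulation of the fixed-participant version (cell of 6, random order, within-person SD 15, participant-by-food SD 10–20, all assumed), the error rate of a nominal 5% food-versus-bread test rose to 9–15%. This objection stands, and the fix below allows for it.

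**Conclusion.** The point holds. The plan expects people to stop early in a within-person design, and its stated method has neither a participant effect nor a rule for their tests. Either default way of running it is inferior to a within-person model on all available AUCs.

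The size is moderate and rests on assumptions. The AUCs at stake are about 9–11% if stoppers finish half their sessions, and about 2% to 19% at 20% attrition over the possible stopping times. The SE is about 5–12% larger with completers only, under assumed SDs. Bias in the ordinary ANOVA is possible but conditional on who stops and on a food order not visible here. The change is worth making before analysis; it does not call the pilot itself into question.

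**What to change.** In section 6.1 A, replace the ANOVA sentence with the following elements.

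- **Analysis set:** every participant with at least one food test.
- **Model:** a linear mixed model (SPSS MIXED) on all available AUCs, with food, group, food-by-group and panel as fixed effects and participant as a random effect. The food-by-group term is needed for the planned intra- and inter-group comparisons. Panel can be separated from food because white bread, the mix in water and the muffin are in both panels.
- **Replicates:** average the two tests of each food, or keep both and add a participant-by-food random effect.
- **Contrasts:** multiplicity-adjusted food comparisons.
- **Sensitivity analysis:** the same contrasts in completers only.

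As a clarification only, state in section 6.3 G that servings eaten and adverse events reported by people who stop are counted.

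The cost is wording: no extra visits, participants or software. The small downside is that the model assumes stopping depends only on observed data. The completers-only analysis gives some indication of how much the results depend on how stoppers are handled.

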#### **B. Hypotheses / Research Question(s)**

We hypothesize that food supplemented with dietary fiber will reduce postprandial glycemic response as compared to a standard meal tolerance test (white bread with 50 g of available carbohydrates). Further, the impact of supplemented food, although with the same amount of dietary fiber, will vary due to differences in cooking procedures and serving temperatures.

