#### **1.3 Research Design and Methods**

**OVERVIEW.** This is a pilot study to characterize the effect of food supplemented with dietary fiber on glycemic response in human. Participants will test 6 food items (plus a control food for comparison) with postprandial glycemic response monitored using a continuous glucose monitoring system. The study will be conducted at the Cook-Douglass Student Health Center and Harvest Café at New Jersey Institute for Food, Nutrition & Health (IFNH). There will be an eligibility screening and group assignment visit, and 14 food testing visits over 4 weeks (Figure 1).

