**GROUP ASSIGNMENT.** Upon confirmation of eligibility, the Research Officer will measure fasting blood glucose concentration (FBG) by performing a finger prick test (ACCU-CHEK® Aviva Plus, Roche Diabetes Care, Indianapolis, IN). Participants who are clinically diagnosed with impaired glucose tolerance or type 2 diabetes (diet-controlled and/or on oral hypoglycemic medications) will be assigned to the Prediabetes/Diabetes group irrespective of their finger prick test results. For participants who are not diagnosed with diabetes, those with FBG < 100 mg/dL will be assigned to the Non-Diabetes group, and those with FBG ≥ 100 mg/dL will be assigned to the Prediabetes/Diabetes group based on classification guidelines from the American Diabetes Association (5). Participants will also be asked to sign up for one of the testing panels: 1) Panel A will test one control food (white bread) and six fiber-supplemented food (dietary fiber mix in water, hot waffle, room temperature waffle, hot pancake, room temperature pancake and muffin); or 2) Panel B will test one control food (white bread) and six fiber-supplemented food (dietary fiber mix in water, sponge cake, crispbread, vegetable smoothie, fruit smoothie and muffin). Finally, the Research Officer will collect information to complete the participant profile, including anthropometry measurements (height and weight), and demographics and contact details.

The eligibility screening and group assignment visit will take approximately 1 h to complete.

**FOOD TESTING.** In the morning of each testing day, participants will attend IFNH between 8 and 10 am after an overnight fast of at least 8 h. They will be required to consume all the study food provided under supervision. The

amount of white bread to be consumed will contain 50 g of available carbohydrates (3-4 slices of bread), and the amount of fiber-supplemented food to be consumed will contain 60 g of dietary fiber mix (approximately 2 waffles, 2 pancakes, 2 slices of sponge cake, 2 serves of crispbread, 2 muffins or 300 ml of smoothies). Participants may leave the research facility after consuming the food, and they will be instructed to refrain from eating and drinking (except water) for the next 3 h. Each food will be tested twice over two consecutive days, with all testing to be completed in 4 weeks (Figure 1). Each food testing session will take approximately 30 min to complete.

[figure not shown]

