### 1.6 Study Variables

#### A. Independent Variables, Interventions, or Predictor Variables

The independent variable will be type of food: white bread vs dietary fiber mix in water, waffle, pancake, sponge cake, crispbread, vegetable smoothie, fruit smoothie and muffin.

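### Serving temperature is part of the second hypothesis and Panel A crosses it with food within person, but neither 1.6A nor 6.1A names it; one planned contrast would be about 2.2 times as precise as a Tukey pair.

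*Combined protocol and SAP*

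**What the plan says.** Section 1.1B has two hypotheses. The second is that the impact of foods carrying the same amount of fiber "will vary due to differences in cooking procedures and serving temperatures".

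Section 1.3 (Group Assignment) gives Panel A white bread and six fiber foods: "dietary fiber mix in water, hot waffle, room temperature waffle, hot pancake, room temperature pancake and muffin". Panel B contains no hot/room-temperature pair. Section 1.3 (Overview) confirms the count: "Participants will test 6 food items (plus a control food for comparison"), so seven foods per person.

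Section 1.6A defines the factor without temperature: "The independent variable will be type of food: white bread vs dietary fiber mix in water, waffle, pancake" and so on, with waffle and pancake listed once each.

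Section 6.1A gives the whole efficacy analysis in one sentence: analysis of variance with a two-tailed Tukey test "will be used for intra-and inter-group comparisons of postprandial blood glucose concentration (area-under-curve"). The criterion is "Statistical significance will be accepted at *p* value < 0.05". It names no temperature term, interaction or planned contrast.

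The completer target in 4.5C is "20 (5 each in Panel A Non-Diabetes group and Prediabetes/Diabetes group, same two groups for Panel B"), which makes 10 in Panel A.

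**The concern.** The menu was built so that temperature is crossed with food inside each Panel A participant. That arrangement lets all four waffle and pancake items contribute to a single within-person estimate of the temperature effect. The variable list and the analysis paragraph do not use it.

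If the analyst does what 6.1A most naturally implies, hot versus room temperature appears only as two separate pairs. Each pair uses half of the temperature data, and each is adjusted as though all 21 food pairs were of equal interest. The study is meant to inform food development for a later trial in type 2 diabetes (1.1A, 1.2). The loss of precision therefore falls on a comparison the protocol set out to make. Naming the contrast beforehand also removes the option of choosing it after the data are seen.

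**Working it through.** **Inputs**
- Foods in Panel A: 6 + 1 control = 7 (1.3), so 7 x 6/2 = 21 pairs.
- Panel A completers: 5 + 5 = 10 (4.5C). The stated total reproduces: 5 x 2 groups x 2 panels = 20.
- Two-sided alpha: 0.05 (6.1A).
- Within-person residual SD of a participant's mean area under the curve for one food: not given, written s. It cancels in the width ratio if the error variance is the same for all foods (assumption).
- Error df for a group-by-food mixed model: (10 - 2) x 6 = 48.
- The plan gives no power or precision figure to reproduce; 1.5 says that no power calculation was done.

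**Interval half-widths, n = 10, df 48**
- One Tukey pair: variance 2s²/10, critical value q/√2 = 3.077. Half-width = 3.077 x s x √(2/10) = 1.376 s.
- Planned contrast, mean of the two hot items minus mean of the two room-temperature items: variance 4 x (1/4) x s²/10 = s²/10, critical value t = 2.011. Half-width = 2.011 x s x √(1/10) = 0.636 s.
- Ratio = 1.376/0.636 = 2.16. It is the product of 3.077/2.011 = 1.53 (Tukey against an unadjusted t) and √2 = 1.41 (averaging over two foods).

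**How far the ratio moves**

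| Setting | Ratio |
|---|---|
| n = 10, groups pooled, df 48 or 54 | 2.16 |
| One glycemic group, n = 5, df 24 (2.031 s against 0.923 s) | 2.20 |
| Tukey over 14 group-by-food cells, pair and contrast both within one group (2.233 s against 0.899 s) | 2.48 |
| Tukey over the four 2 x 2 cells only | 1.89 to 1.93 |
| n = 10, contrast on its own error term, df 8 or 9 | 1.89 to 1.92 |
| n = 10, three contrasts, Bonferroni, pooled error | 1.75 |
| n = 10, three contrasts, Bonferroni, own error term | 1.44 to 1.48 |
| n = 5, contrast on its own error term, df 4 | 1.64 (1.15 with Bonferroni over three) |

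**Power, n = 10, df 48, same temperature effect in both foods**
- The contrast has 80% power at 0.904 s (noncentral t).
- At 0.904 s, one Tukey pair has 16% power. The chance that at least one of the two temperature pairs is significant is 29%; that both are, 3%.
- At 1.5 s, one Tukey pair has 61% power; at 2 s, 91%.

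**The case against.** **The plan does not say that it tests temperature by Tukey pairs.** This is right. Section 6.1A mentions neither temperature nor the number of levels, and analysis of variance does not exclude a factorial model. A reader might infer that the protocol chose single Tukey pairs for this hypothesis. The text supports only that temperature is missing from 1.6A and 6.1A, and that Tukey pairs among the foods are the natural reading of what is there.

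**The 2.2 is not entirely like for like.** Also right. The factor of 1.41 comes from estimating an average effect over two foods instead of the effect in one food. The comparator is a single unadjusted contrast on pooled error. The simple differences within waffle and within pancake, left unadjusted, have half-width 2.011 x s x √(2/10) = 0.899 s, which gains only the factor of 1.53.

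**The 16% is selective.** In part. It is the power of one pair at an effect chosen to give the contrast 80%; allowing either pair to count gives 29%. A reader might infer that a true temperature effect would usually be missed and reported as no difference. The documents give no SD and no expected temperature effect, and at 2 s a single pair would detect it 91% of the time, so that inference is unsupported.

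**Ten is an assumption.** Section 6.1A speaks of comparisons within and between groups, and each glycemic group has 5 per panel. Within one group the ratio hardly changes on pooled error (2.20), but the contrast itself is less precise (0.923 s).

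**The crossing may not be clean.** Each food is tested on two consecutive days over four weeks, with a sensor change after 14 days, and the available text does not state the food order. If the order is fixed, temperature could be mixed with week or sensor. That would affect Tukey pairs and the contrast alike; a narrower interval does not remove it.

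**It is a pilot for choosing foods.** Item-by-item differences are a fair target, and the white-bread hypothesis is untouched. But a fixed small sample is a reason to use the 2 x 2, and the simple differences can still be reported.

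**Conclusion.** The point holds as a gap between a stated hypothesis and the analysis. Temperature is hypothesized in 1.1B and crossed with food in Panel A, but it is absent from 1.6A and 6.1A.

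If 6.1A is read as Tukey over the seven Panel A foods, each of the two temperature pairs has an interval about 2.2 times as wide as one planned contrast. This assumes 10 completers with both glycemic groups pooled, a common error variance and one unadjusted contrast. Under other reasonable choices at n = 10 the ratio is about 1.4 to 1.9, and about 2.5 if Tukey spans the 14 group-by-food cells. The contrast is narrower in every setting checked, though only slightly (1.15) in the strictest one, with n = 5. The change is worth making, but the first hypothesis does not depend on it.

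**What to change.** In 1.6A, list serving temperature (hot, room temperature) as a variable for the Panel A waffle and pancake.

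In 6.1A, add for Panel A: 'Serving temperature will be tested by one planned within-participant contrast, (hot waffle + hot pancake)/2 minus (room-temperature waffle + room-temperature pancake)/2, two-sided at 5%, adjusted for glycemic group. The food-by-temperature interaction and the two simple differences will be reported with 95% confidence intervals as descriptive results.' State which error term the contrast uses. Keep Tukey's test for the other food comparisons.

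The cost is wording only: no added participants, visits or measurements. The drawback is that the contrast estimates an average effect, so it is less informative if temperature acts in opposite directions in waffle and pancake. The reported interaction would show this, though imprecisely: the difference between the two simple differences has half-width 2.011 x s x √(4/10) = 1.272 s.
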